12. Visual acuity best correctable to 20/25 or better for each eye
13. The subject must read and sign the Informed Consent form.
14. No active conditions that may prevent soft contact lens wear.
15. Not habitual wearer of any of the test lenses.
16. Photopic pupil size ≥ 4 mm (normal room illumination ~ 100 cd/m²)

SAMPLE SIZE DETERMINATION

The comparison of interest is DT1 sphere and DT1 MF Lo add, so the sample size calculation was based on detecting a difference between these 2 lenses.

1. The proposed study design is a 2 x 2 crossover design balanced for residuals with four sources of variation: lens, sequence group, period and participant. The same number of participants will be randomized to each of two possible lens sequence groups: {A, B}, {B, A}. Because each lens is preceded by every other lens exactly twice we can check for lens carryover effects; if the carryover effect is the same for each lens type, these effects cancel when comparing differences in lens means.
2. The primary outcome measures are difference in subjective ratings for the current trial lenses normalized to the ratings made at baseline wearing habitual lenses, i.e., ratings will be assessed using an integer scale of 0-100 with semantic anchoring and the rating at baseline will be subtracted from the rating made with each one of the three trial lenses.

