3. Ideally, the sample size analysis would incorporate 'known' estimates of the mean, variance and (autoregressive) covariance of subjective ratings for the habitual and each of the three study lenses measured in a comparable experimental design to the proposed three-arm crossover study. Here, we rely on ratings data from previous CORL studies to inform the power analysis. Specifically, we have typically observed (1) individual differences in baseline ratings with habitual lenses, (2) period effects such that ratings that are, on average, lower and also more variable at follow-up assessments, and (3) moderate to strong within-participant correlations in ratings assessed with different study lenses. A limitation of the previous data is that that we have typically observed non-significant LENS*PERIOD interactions in the fitted linear mixed regression models. So, for the current analysis, we base the effect size for the *a priori* power analysis on a desired (i.e., clinically relevant) pairwise difference of 9 units in subjective rating. Previous data suggests that the expected variability (σ) in ratings during follow-up assessments is ~ 15 -19 rating units with correlations ranging from 0.50-0.60.
4. To arrive at the initial (unadjusted) sample size estimate, we performed a power analysis for a within-participants comparison of the mean difference in the normalized ratings (i.e., change re: rating at baseline wearing pristine habitual lens) for two study lenses. Specifically, although we will initially fit linear mixed effects models to the data and obtain least-squares estimates of the pairwise mean differences in rating, we can the required sample size to power a *paired-samples t test* for normal (continuous) mean difference

Note that the paired-sample t test assumes normally distributed data and requires $N \geq 2$. The test statistics are

$$t = N^{1/2} \left(\frac{\bar{d} - \mu_0}{s_d} \right) \sim t(N - 1, \delta) \text{ or, equivalently, } t^2 \sim F(1, N - 1, \delta^2)$$

where \bar{d} and s_d are the sample mean and standard deviation of the differences, and

$$\delta = N^{1/2} \left(\frac{\mu_{diff} - \mu_0}{\sigma_{diff}} \right) \text{ and } \sigma_{diff} = (\sigma_1^2 + \sigma_2^2 - 2\rho\sigma_1\sigma_2)^{1/2}$$

represent the non-centrality parameter and standard deviation of the paired difference scores, respectively.

[figure not shown]

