- Our calculation assumed a standard deviation of 18 rating units. With equal variances, the estimated $\sigma_{diff} = (\sigma_1^2 + \sigma_2^2 - 2\rho\sigma_1\sigma_2)^{1/2} = 18\sqrt{2 * (1 - \rho)}$. We varied both the sample mean between 7 and 12 units in steps of 1 unit and the within-participant correlation between 0.40 and 0.60 in steps of 0.05 to compute the number of pairs of observations needed to achieve a minimum of 80% power at significance level of $\alpha=0.05$ and a non-directional test ($H_0 \neq 0$ mean difference). **Table 1 and Figure 1** show the results under this scenario. In **Table 1**, rows corresponding to a mean rating difference of 9 units are enclosed in the box. For correlation of 0.50, the estimated number of participants required to detect a moderate effect size of $9/18=0.50$ is 34. Because we want to balance the design for residuals, a total sample size of $N=36$ (unadjusted for dropout) is needed to assign 6 participants to each sequence group. To detect the same effect size with slightly weaker correlations the sample size should be increased to $N=42$. **Figure 1** shows that rating differences ≥ 9 units could be detected for correlations ≥ 0.40 with sample of 40 or fewer participants.

Table 1

Index	Computed N Pairs		Actual Power	N Pairs
	Mean Difference	Correlation		
1	7	0.40	0.805	65
2	7	0.45	0.807	60
3	7	0.50	0.801	54
4	7	0.55	0.803	49
5	7	0.60	0.805	44
6	8	0.40	0.803	50
7	8	0.45	0.803	46
8	8	0.50	0.803	42
9	8	0.55	0.803	38
10	8	0.60	0.803	34
11	9	0.40	0.804	40
12	9	0.45	0.806	37
13	9	0.50	0.808	34
14	9	0.55	0.810	31
15	9	0.60	0.814	28
16	10	0.40	0.806	33
17	10	0.45	0.801	30
18	10	0.50	0.809	28
19	10	0.55	0.802	25
20	10	0.60	0.812	23
21	11	0.40	0.812	28

22	11	0.45	0.815	26
23	11	0.50	0.818	24
24	11	0.55	0.802	21
25	11	0.60	0.804	19
26	12	0.40	0.815	24
27	12	0.45	0.811	22
28	12	0.50	0.807	20
29	12	0.55	0.802	18
30	12	0.60	0.822	17

Figure 1

Based on this, we aim to enroll 44 subjects, so as to complete 42 throughout the study duration.

LENSES

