The spherical power of all corrections will be monocularly, distance vision optimized. Specifically, lens powers may not be the same for all types of lenses, due to power-targeting during manufacture, on-eye flexure, etc. Optimization entails providing the lens for each eye that monocularly provides an objective improvement in acuity and up to -0.25 D more for any patient-reported quality improvement. All lenses will be over-labeled, so as to, as best as possible, preserve masking (less blister pack shape). Of note, subjects will not be able to tell the difference between DT1 and DT1 MF (Lo add) because of the same blister shape, but may be able to tell a difference between these and habitual.

OUTCOME MEASURES

Primary:

1. Subject-reported eye fatigue (0-100 rating scale, 0=optimal)

STATISTICAL ANALYSIS

Our primary analysis will use SAS PROC MIXED (or R LMER) to fit linear mixed effects model to the normalized change from baseline ratings data. Because the proposed design is balanced for residuals we could fit the data using PROC GLM if there are no missing data to obtain identical parameter estimates. A separate model will be fit to the data for each rating scale tested. All four sources of variation (lens, sequence group, period and participant) will be included as class variables. We will also test for a carryover effect by including a character-valued variable whose value represents the lens worn in the previous period ('0' assigned to the carryover variable for the first period). Thus, the initial models used to analyze the data include effects for sequence group, lens, period and the overall carryover. Participant-within-sequence group will be included as a random effect. Although LSMEANS due to lens will not be estimable in these models, differences between trial lenses are if we assume the carryover effect is the same for each lens type. Evidence of a significant Lens-by-Period interaction will be handled by running separate analyses within each period using, for example, a *two-sample independent samples t-test*.

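### In a two-sequence AB/BA crossover with sequence, lens and period fitted, the previous-lens carryover term has 0 df, so the planned test cannot be computed, and no final model is named for Hypotheses 1-2

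*Combined protocol and SAP*

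**What the plan says.** STUDY DESIGN and SAMPLE SIZE DETERMINATION item 1 fix two sequences, {A, B} and {B, A}, with equal allocation. The habitual-lens baseline always comes first. The response is the change from that baseline, so each participant contributes two values.

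On the model, STATISTICAL ANALYSIS says: "All four sources of variation (lens, sequence group, period and participant) will be included as class variables". It then adds a variable holding the lens worn in the previous period (coded '0' in period 1) to test for carryover, and sums up: "Thus, the initial models used to analyze the data include effects for sequence group, lens, period and the overall carryover". Participant within sequence is random.

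On what can be estimated, it says: "Although LSMEANS due to lens will not be estimable in these models", but "differences between trial lenses are if we assume the carryover effect is the same for each lens type".

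On switching, it says: "Evidence of a significant Lens-by-Period interaction will be handled by running separate analyses within each period", with a two-sample t-test as the example.

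The reason given for being able to check carryover is in SAMPLE SIZE DETERMINATION item 1: "Because each lens is preceded by every other lens exactly twice we can check for lens carryover effects". Later in that section, a total of N=36 "is needed to assign 6 participants to each sequence group".

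Hypotheses 1 and 2 (PROTOCOL SYNOPSIS) are that the mean change from baseline is below 0 for lens A and for lens B. Hypothesis 3 is that B-A is below 0.

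**The concern.** A crossover with two sequences and two periods has four cell means and therefore supports four fixed-effect parameters. The plan asks for sequence, lens, period and previous lens together, which is more than the design can separate. The carryover check is presented as a safeguard. If it has no degrees of freedom, the software will drop the term or report no test, and the safeguard is absent without anyone having decided so.

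Two of the three hypotheses also concern a lens mean rather than a lens difference. The plan says those means are not estimable in its starting model, and it gives no rule for dropping carryover and no final model. The two-sample fallback compares A with B, not either lens with baseline. How Hypotheses 1-2 will be tested is left to be settled after the data are in.

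**Working it through.** **The plan's own figure.** Paired t-test, difference 9, SD 18, correlation 0.50, two-sided 0.05: SD of the difference = 18·√(2(1−0.5)) = 18, and N=34 gives power 0.808. This matches Table 1, as do the other 29 rows.

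**Degrees of freedom.** Order the cells AB period 1 (lens A), AB period 2 (lens B), BA period 1 (lens B), BA period 2 (lens A), and code each effect ±1:

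- sequence: (+1, +1, −1, −1)
- lens: (+1, −1, −1, +1)
- period: (+1, −1, +1, −1)

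With the intercept these span all four cells (rank 4). Then:

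- The preceded-by-A minus preceded-by-B contrast is (0, +1, 0, −1) = (sequence − lens)/2. It adds nothing: rank 4, 0 df.
- Lens × period is (+1, +1, −1, −1), which is the sequence column: rank 4, 0 df.
- Carryover common to both lenses is (0, 1, 0, 1), which is a recoding of period: not testable.

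Without sequence, lens + period has rank 3, and adding carryover, lens-by-period or sequence each gives rank 4. The 1 df gained supplies the same sequence contrast each time.

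**Fit with the stated justification.** In AB/BA each lens is preceded by the other in one sequence only, not two. N=36 with 6 per group implies 36/6 = 6 groups; two groups would have 36/2 = 18. Both statements fit three lenses in six sequences, where adding carryover raises the rank from 10 to 12 and so gives 2 df.

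**Estimability.** With carryover in the model, the LSMEANS for A and B (default equal weights) are not estimable, whether or not sequence is kept. With sequence + lens + period only, LSMEAN A, LSMEAN B and B-A are all estimable. In that model LSMEAN A averages AB period 1 and BA period 2, so it contains half of any carryover from B and the whole of any trend since baseline that is common to both periods. A common trend and equal carryover cancel from B-A.

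**Power of the sequence contrast.** With 21 per sequence, SE = SD·√(2(1+ρ)·2/21), 40 df. For a 9-unit carryover difference at SD 18:

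| ρ | SE | Power |
|---|---|---|
| 0.4 | 9.30 | 15.7% |
| 0.5 | 9.62 | 15.0% |
| 0.6 | 9.94 | 14.3% |

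Over SD 15-19 the range is 13-21%.

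**Period-1 A versus B at 9 units.** SE = 18·√(2/21) = 5.55, 40 df: 35% power (32% at SD 19, 48% at SD 15).

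**Switching at 5% on the sequence contrast, no lens effect, no carryover.** From 400,000 simulated trials per ρ, for ρ = 0.4, 0.5, 0.6:

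- B-A declared in 7.1%, 7.4%, 7.6% if the period-1 test is used after switching.
- B-A declared in 8.9%, 9.1%, 9.3% if either period's test counts.
- Among switched trials the period-1 test rejects in 48-57%, because the two contrasts are strongly correlated.

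**Hypothesis 1 when lens A has no effect (illustration only).** SE = 18/√42 = 2.78, 40 df. Bias is half the carryover from B.

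- Carryover of −1, −2, −4, −6 units: two-sided rejection 5.4%, 6.4%, 10.8%, 18.4% (5-24% over carryover −1 to −6 and SD 15-19).
- Baseline-to-follow-up trend of −1, −2, −3 units, no carryover: 6.4%, 10.8%, 18.4% (6-24% over SD 15-19).

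**Powered comparison.** B-A of 9 units, N=42, SD 18: 82%, 89%, 94% for ρ = 0.4, 0.5, 0.6.

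**The case against.** The rank result is not disputable, but its reach can be.

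- **The sequence term already carries the contrast.** In AB/BA the sequence effect is the lens-by-period contrast, and the plan fits sequence. This is true, but the plan does not name sequence as the carryover test or as the switching trigger, so the tests it does name remain uncomputable.
- **The inflated error rate belongs to a procedure the plan does not state.** It arises only if sequence is dropped or used as the trigger, and counting either period is one reading of an unspecified rule. This stands: the 7.1-9.3% is conditional.
- **The time trend affects every model.** Baseline comes first by design, so the recommended model does not remove the trend. This also stands. It is a reason to state the assumption, not a measure of the harm from the 0-df term. The plan itself reports "period effects such that ratings that are, on average, lower and also more variable at follow-up assessments", so the assumption is not trivial.
- **The SD may refer to raw ratings.** If 15-19 describes raw ratings and ρ also links baseline to follow-up, the change-score SD is 18·√(2(1−ρ)) and the correlation between changes is 0.5. Period-1 power is then 30-42% and sequence-contrast power 13-18% at SD 18. Both remain low.
- **The natural reading is the four-source model.** The plan lists those terms first and calls the carryover models initial. That is plausible, and both lens means are estimable there, but the plan never says so and gives no rule for getting from one model to the other.

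**Conclusion.** The concern holds. The 0-df result is algebra: it needs no assumption about variances or sample size, only the two sequences, two periods and change-score response that the plan specifies. As written, neither the carryover test nor the Lens-by-Period trigger can be computed with sequence in the model, and the stated reason for being able to check carryover does not describe this design. Hypotheses 1-2 have no stated final model and rest on two unstated assumptions: negligible carryover and no trend from the baseline period.

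The sizes are conditional. The documents give no carryover size, trend or separately identified change-score SD; 18 and 15-19 come from SAMPLE SIZE DETERMINATION, and the carryover and trend values are assumed ranges. Hypothesis 3, the powered comparison, is estimable under the plan's equal-carryover assumption, and the sample size stands. This should be fixed before analysis, but it does not threaten the conduct of the trial.

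**What to change.** In STATISTICAL ANALYSIS:

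1. Delete the previous-lens variable and its test, the Lens-by-Period switching rule, and the sentence on non-estimable LSMEANS.
2. Name one primary model: fixed lens, period and sequence, with random participant-within-sequence. Take Hypothesis 3 from the B-A contrast and Hypotheses 1-2 from the lens LSMEANS tested against 0.
3. State that the only check on unequal carryover is the between-participant sequence contrast, that it is aliased with lens-by-period, that it has about 15% power for a 9-unit carryover difference (assumed SD 18, ρ 0.4-0.6), and that it will not be used to choose the analysis. State that equal carryover is aliased with period and cannot be tested.
4. Keep the period-1 A-versus-B comparison only as a sensitivity analysis, giving its power (about 35% at 9 units, SD 18) together with the SD assumption.
5. State the assumptions: equal carryover for Hypothesis 3; negligible carryover and no time trend from baseline for Hypotheses 1-2.

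In SAMPLE SIZE DETERMINATION, remove the claim in item 1 about how often each lens precedes the others, keeping the equal-carryover assumption stated. Correct the number per sequence group to fit two sequences (18 each at N=36, 21 each at N=42).

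The cost is SAP wording only; sample size, visits and conduct do not change. What is given up is a carryover check that the design could not deliver, and a within-period fallback that becomes a low-power sensitivity analysis.

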STUDY DESIGN	
The proposed study design is a subject masked, 2 x 2 randomized, crossover (with a baseline reference) comparing the difference in fatigue rating relative to baseline, where the baseline the is the response for subject habitual lenses, with optimized power, worn on their typical (e.g. 2 week, 1 month) replacement schedule. The study design is balanced for residuals with four sources of variation: lens, sequence group, period and participant. To adjust for individual differences prior to study entrance, difference scores will be used as response variables in the analyses. The same number of participants will be randomized to each of two possible lens sequence groups: {A, B}, {B, A}. Baseline will be evaluated prior to any testing of A and B. Specifically, A and B are:
 
Baseline = Subject habitual lenses, with optimized power, habitual replacement A = DAILIES TOTAL 1 sphere (DT1) B = DAILITES TOTAL 1 MULTIFOCAL (DT1 MF)
 
Subjects will be randomized into two equal groups of those that have each of the two sequences ({A, B}, {B, A}) (balanced Latin Square design).

STATISTICAL CONSIDERATIONS	
Sample size	N=42
Hypothesis	
 1. Subject-reported eye fatigue difference scores (lens A – baseline) comparing the change in response for lens A to baseline are <0 (i.e. fatigue rating was improved with lens A over baseline). This hypothesis tests if a lens with enhanced surface (DT1) provides better fatigue ratings than a typical lens without an optimized surface (optimized habitual). 2. Subject-reported eye fatigue difference scores (lens B – baseline) comparing the change in response for lens B to baseline are <0 (i.e. fatigue rating was improved with lens B over baseline). This hypothesis tests if a lens with enhanced surface and enhanced optics (DT1 MF) provides better fatigue ratings than a typical lens without an enhanced surface or enhanced optics (optimized habitual). 3. Subject-reported eye fatigue difference scores (lens B – lens A) comparing the difference in response for lens B to lens A are <0 (i.e. fatigue rating was improved with lens B over lens A). This hypothesis tests if a lens with enhanced surface AND enhanced optics (DT1 MF) provides better fatigue ratings than a lens with only enhanced surface (DT1) characteristics.

Data analysis	SAS PROC MIXED (or R LMER) to fit linear mixed effects model to the normalized ratings data.

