Furthermore, a recent double-masked, randomized, bilateral cross-over study of pre-presbyopic subjects (Orsborn GSLS 2016) indicates that when two lenses of the same material are compared, one with typical single vision optics and one with optimized optics to decrease accommodative need, individuals report no change in the surface or dryness component of their eye fatigue, but do report a decrease in the optical components of eye fatigue (such as straining). Accordingly, DAILIES TOTAL 1 multifocal, as a single use lens with optimized surface qualities and optimized optics, may be a lens capable of ameliorating eye reported eye fatigue by acting on both the surface and optical sensations that are believed to be the largest components of eye fatigue ([name] 2016).

The current proposal briefly outlines potential strategies to systematically investigate the questions highlighted above. If the results are favorable, the results may serve to help practitioners understand how the DAILIES TOTAL 1 family of products may help ameliorate symptoms of digital eye fatigue.

AIM: To quantify the real-time subject-reported fatigue in symptomatic, non-daily replacement silicone hydrogel soft contact lens wearers and the change in symptomology associated with change to DAILIES TOTAL 1 (sphere), DAILIES TOTAL 1 multifocal (LO Add), relative to normal replacement of habitual lens.

1. No diagnosis of dry eye or ocular surface disease
2. Corneal plane cylinder less than or equal to 0.75 D
3. No diagnosis of any accommodative or convergence problem

METHODS:

STUDY DESIGN: The proposed study design is a subject masked, 2 x 2 randomized, crossover (with a reference) comparing the difference in fatigue rating relative to baseline, where the baseline is the response for subject habitual lenses, with optimized power, worn on their typical (e.g. 2 week, 1 month) replacement schedule. The study design is balanced for residuals with four sources of variation: lens, sequence group, period and participant. To adjust for individual differences prior to study entrance, difference scores will be used as response variables in the analyses. The same number of participants will be randomized to each of two possible lens sequence groups: {A, B}, or {B, A}. Baseline will be evaluated prior to any testing of A and B. Specifically, A and B are:

Baseline = Subject habitual lenses, with optimized power, habitual replacement

A = DAILIES TOTAL 1 sphere

B = DAILITES TOTAL 1 MULTIFOCAL

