The analysis will not specifically make p-value adjustment for multiple testing as the comparisons are planned in advance. The omnibus in an (M)ANOVA or parameter estimates for a factor in a Linear Mixed-Effects regression model provide the protection against "family-wise" error, i.e., once the omnibus test (or saturated model) detects an effect at say $\alpha=0.05$, doing subsequent pairwise comparisons on different levels of the factor(s) can no longer generate a false alarm (Type I error)!

Having said that, as a follow-up, exploratory technique, we may also use Dunnett's method for performing all pairwise comparisons of the means and other margins across levels of our categorical variables (e.g., lens) after model estimation. This method adjusts the p-values and confidence intervals for multiple comparisons involving a fixed reference category (i.e., the control lens).

PUBLICATION PLAN: Work will be presented at least one international meeting, such as Global Specialty Lens Symposium or ARVO. The work will also be prepared for submission for peer-reviewed publication (e.g. Optometry and Vision Science). Trade publications may also be prepared at Sponsor's request and expense.

TIMELINE: (estimated)

Contract approval: unknown, estimate 1 month

Human subjects approval: 1 month, concurrent to above

Project setup: 1.5 month, concurrent to above

Recruitment: 1 month

Data collection: 3 months

Data analysis: 3 months

Report writing: 3 months

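### The claimed omnibus protection against Type I error is false, and in the change-from-baseline model the lens test is Hypothesis 3 alone, so Hypotheses 1 and 2 have no workable protection

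*Combined protocol and SAP*

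**What the plan says.** The Hypothesis row of the Protocol Synopsis lists three directional hypotheses, with no order and no primary or secondary label:

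- H1, A minus baseline: "comparing the change in response for lens A to baseline are <0".
- H2, B minus baseline: "comparing the change in response for lens B to baseline are <0".
- H3, B minus A: "comparing the difference in response for lens B to lens A are <0".

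Under Study Design, participants are randomised to one of two orders of A and B, and "Baseline will be evaluated prior to any testing of A and B". The primary analysis will "fit linear mixed effects model to the normalized change from baseline ratings data", with sequence group, lens, period and carryover as effects and participant as a random effect.

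On multiplicity, the Statistical Analysis section states: "The analysis will not specifically make p-value adjustment for multiple testing as the comparisons are planned in advance". It then credits the omnibus test with family-wise protection and says that after it "doing subsequent pairwise comparisons on different levels of the factor(s) can no longer generate a false alarm (Type I error". Dunnett's method against a control lens is mentioned only as a possible exploratory follow-up.

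**The concern.** Two things are wrong. First, no preliminary test makes the tests after it free of error. A significant omnibus result shows that some difference probably exists, not that every difference found later is real. Planning comparisons in advance does not control family-wise error either.

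Second, the usual defence of this kind of gate does not apply. A strict omnibus test across three conditions does protect the three pairwise comparisons among them, but only if all three conditions are levels of the factor tested. Here the habitual lens has been moved into the response. What remains is a two-level factor whose test is H3, so H1 and H2 are not comparisons between its levels.

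H1 and H2 carry the claim that the new lenses beat the habitual lens. Depending on how the paragraph is read, that claim is either made with inflated error or blocked in a favourable and plausible scenario. The plan does not fix the reading, so it could be chosen after the data are seen.

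**Working it through.** **Inputs** (Sample Size Determination): SD 18 rating units; correlation 0.50, with a grid of 0.40 to 0.60; clinically relevant difference 9 units; two-sided alpha 0.05; 42 completers. *Assumptions not in the plan:* baseline has the same SD and correlation as A and B; there are no period or carryover effects.

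**1. The plan's own figure.** SD of a paired difference = 18 × √(2 × (1 − 0.50)) = 18. With N = 34 the non-centrality is √34 × 9/18 = 2.92, and the exact paired-t power is 0.808, as in Table 1. With N = 42 the power is 0.886. The plan gives no family-wise error figure to reproduce.

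**2. What the lens test tests.** The design has four sequence-by-period cells. The fixed-effect matrix for intercept, sequence and period has rank 3. Adding lens gives rank 4, so lens has one degree of freedom, the A versus B contrast (H3). If the carryover variable is already in the model with separate values for the previous lens, the rank is already 4 and lens adds nothing. The test therefore exists only if carryover is assumed equal, as the plan acknowledges. H1 and H2 concern mean changes for single lenses, and the plan itself says that lens means cannot be estimated in its initial models.

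**3. Reading (i): H1, H2 and H3 each tested at 0.05, no gate.** The three contrasts share data, so the error rate was simulated with paired t-tests. With no true differences, at correlation 0.50:

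- at least one false positive among the three: 12.3% two-sided, 12.7% one-sided at 0.05;
- at least one among H1 and H2: 9.1% two-sided.

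Across correlations 0.40 to 0.60 the two-sided any-of-three figure stays between about 12% and 12.5%. For reference, three independent tests would give 1 − 0.95³ = 14.3%.

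**4. Reading (ii): H1 and H2 tested only after a significant lens effect.** Family-wise error is then about 5%. If A and B differ, at most one of H1 and H2 can be a true null; if they do not differ, the gate opens in only 5% of trials. That same 5% caps the power for H1 and H2 when A and B perform equally, whatever the benefit and whatever N. With both lenses truly 9 units better than baseline:

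| Correlation | H1 or H2 (each), ungated | H1 or H2 (each), gated on lens |
|---|---|---|
| 0.40 | 82% | 3.6% |
| 0.50 | 89% | 3.9% |
| 0.60 | 94% | 4.3% |

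**5. Direct check of the sentence.** Let A equal baseline and B be 9 units better, so that H1 is a true null (correlation 0.50). Among trials that pass the lens test, H1 is still falsely rejected in 4.3%. Among trials that pass a three-level omnibus on raw ratings, it is falsely rejected in 5.4%. The sentence fails under either model.

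**The case against.** The strongest reply is that Sample Size Determination calls the A versus B contrast the comparison of interest and powers only that. If H3 is the sole primary test, its 5% level is intact and the inflation is confined to H1 and H2 as further claims. This is correct, and it limits the damage. But the Synopsis lists the three hypotheses as equals and no section ranks them, so the remedy is to state the ranking.

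Second, a strict H3 gate does control family-wise error. This stands: the defect under that reading is lost power, not excess error, and no single reading has both defects.

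Third, the mention of a control lens as reference category suggests a model with three lens levels. On raw ratings, with a strict omnibus gate, that would hold family-wise error near 5%. It is not the model written in the plan, and the sentence would still be false.

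Fourth, the Synopsis gives a key endpoint of superiority by more than 8 units. If success also required an observed difference above 8 (an assumption), any-of-three error would be about 1.1% at correlation 0.50, and power at a true 9-unit benefit about 63 to 66% across the correlation grid. The hypotheses themselves are stated against zero, so the 12.3% applies to them as written.

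Finally, the Dunnett step is optional and exploratory. That point is minor, though the step also needs baseline as a lens level.

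**Conclusion.** The concern holds. The sentence is wrong as a matter of principle, and the only lens test in the planned model is H3. H1 and H2 are left with either no control (family-wise error about 12.3%, more than double the nominal 5%, if all three are confirmatory) or a gate that stays shut when both lenses help equally (about 4% power instead of 89%). That second scenario is plausible on the plan's own rationale, because A and B share the surface that is hypothesised to relieve dryness.

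The error rates hardly move over correlations of 0.40 to 0.60; the ungated power ranges from 82% to 94%. The figures rest on equal SDs and correlations across baseline, A and B, although the plan expects follow-up ratings to be more variable, and on no period or carryover effects. The powered A versus B comparison is not invalidated. This should be corrected before analysis.

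**What to change.** - Delete the sentence claiming that later comparisons cannot produce a Type I error, and the argument that pre-planning removes the need for adjustment.
- Name H3 as the single primary test at two-sided 0.05, in line with the sample size section, and label H1 and H2 secondary or descriptive. This costs H3 nothing.
- If all three are to remain confirmatory, apply Holm across H1 to H3 at two-sided 0.05. Simulated family-wise error is then about 4.5% when nothing differs. With both lenses 9 units better than baseline, power for each of H1 and H2 falls from 89% to about 80% at correlation 0.50 (71% at 0.40, 89% at 0.60).
- For H1 and H2 in either role, specify the model or test that estimates the mean change for each lens, since the initial models do not.
- Drop the Dunnett sentence, or apply the method in a model of raw ratings with baseline as a third lens level.

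These are changes to the analysis text. Naming H3 as sole primary needs no change in sample size; the Holm option at 42 completers accepts the power loss shown.
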